12.5.3 Patient reported outcomes

SF-36

The following variables will be evaluated:

- SF-36 domain scores (based on a scale of 0-100)
- SF-36 PCS (norm-based scores)
- •

For the change in SF-36 summary scores (PCS), summary statistics will be provided using observed data for each treatment regimen.

The SF-36 domain scores will be summarized by treatment.

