| | The secondary efficacy variables are described below. Secondary efficacy variables will be |
| | analyzed using the FAS population. Handling of missing data for secondary variables will be |
| | the same as for the primary variable. |
| | Safety analysis will include summaries of Adverse Events (AEs), laboratory measurement, |
| | ECG, and vital signs |
| | Full details of data analysis will be specified in statistical analysis plan |
| Key words | Psoriatic Arthritis, PsA, subcutaneous, secukinumab in prefilled syringe, Secukinumab, |
| | AIN457 |

1 Introduction

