| • To evaluate the efficacy of secukinumab 150 mg s.c. (q1w×4, followed by dosing q4w) at Week 16 compared with placebo by assessing the changes from BSL in medical outcome short form health survey - physical component summary(SF36-PCS). | • Change from BSL in SF36-PCS at Week 16. |
| • To evaluate the efficacy of secukinumab 150 mg s.c. (q1w×4, followed by dosing q4w) at Week 16 compared with placebo by assessing the changes from BSL in Health Assessment Questionnaire - Disability Index (HAQ-DI [©]). | • Change from BSL in HAQ-DI [©] at Week 16. |
| • To evaluate the overall safety and tolerability of secukinumab 150 mg s.c. (q1w×4, followed by dosing q4w). | Physical examination, vital signs, laboratory values, AEs/SAEs. |

2.1 **Primary estimands**

The clinical question of interest is: What is the effect of secukinumab 150 mg s.c. versus placebo on the composite endpoint ACR20 response at Week 16 and the completion of 16 week-treatment in Chinese patients with active PsA?

The justification for targeting this treatment effect is that we wish to estimate the effect of the study drug for the full duration when administered without dose changes.

The primary estimand is described by the following attributes:

- a. Population: defined through appropriate inclusion/exclusion criteria to reflect the targeted PsA population
- b. Variable: composite of remaining on the study and on randomized treatment through 16 weeks and achieving ACR20 response at 16 weeks
- c. Intercurrent event: the intercurrent event of discontinuation from treatment or study prior to Week 16 has been addressed via the composite variable definition
- d. Population-level summary: difference in proportions of responders between secukinumab and placebo groups

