2.2 Secondary estimands

The clinical questions of interest are:

- What is the effect of secukinumab 150 mg s.c. versus placebo on the composite endpoint ACR50 response at week 16 and the completion of 16 week-treatment in Chinese patients with active PsA?
- What is the effect of secukinumab 150 mg s.c. versus placebo on change from BSL in DAS28-CRP at week 16 in Chinese patients with active PsA had patients completed 16 week-treatment?
- What is the effect of secukinumab 150 mg s.c. versus placebo on change from BSL in PASDAS at week 16 in Chinese patients with active PsA had patients completed 16 week-treatment
- What is the effect of secukinumab 150 mg s.c. versus placebo on change from BSL in SF-36 PCS at week 16 in Chinese patients with active PsA had patients completed 16 weektreatment?
- What is the effect of secukinumab 150 mg s.c. versus placebo on change from BSL in HAQ-DI at week 16 in Chinese patients with active PsA had patients completed 16 week-treatment?

The justification for targeting the treatment effect is that we wish to estimate the effect of the study drug for the full duration when administered without dose changes.

The estimand definition of all secondary objectives related to response (e.g., ACR50, etc.) will have the same attributes as that for the primary estimand, except for the variable of interest.

Estimand definition for the secondary continuous variables (e.g., $HAQ-DI^{\odot}$, etc.) is the following:

- a. Population: defined through appropriate inclusion/exclusion criteria to reflect the targeted PsA population
- b. Variable: change from BSL in the variable of interest
- c. Intercurrent event: discontinuation from treatment or study prior to Week 16
- d. Population-level summary: difference in variable means between secukinumab and placebo groups

3 Study design

This bridging study uses a randomized, double-blind, placebo-controlled, parallel-group design. A screening period running up to 10 weeks before randomization will be used to assess participant eligibility followed by 52 weeks of treatment.

At BSL, approximately 40 Chinese participants whose eligibility is confirmed will be randomized to one of two treatment groups in 1:1 ratio:

• Group 1 - secukinumab 150mg s.c. :

Secukinumab 150 mg (1.0 mL PFS of 150 mg dose) administered at BSL, Weeks 1, 2, and 3 followed by dosing every four weeks starting at Week 4.

• Group 2 - placebo s.c.

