12.4.3 Handling of missing values/censoring/discontinuations

Missing data for ACR20 response and other binary efficacy variables (e.g., ACR50, etc.) for data up to Week 16 will be handled as follows:

- 1. participants who discontinue from treatment or study for any reason will be considered as non-responders from the time of discontinuation through Week 16
- 2. participants who do not have the required data to compute ACR responses (i.e., tender and swollen joint counts and at least three of the five ACR core set variables) at BSL and at the specific timepoint will be classified as non-responders at the specific timepoint.

participants who are unblinded prior to the scheduled time point will be considered nonresponders from the time of unblinding up to Week 16. The primary analysis will use the nonresponder imputation.

Continuous variables (e.g., ACR components, etc.) will be analyzed using a mixed-effects model repeated measures (MMRM) which is valid under the missing at random (MAR) assumption. As such, single-point imputation of missing data will not be performed (e.g., LOCF). For analyses of these parameters, if all post-BSL values are missing then these missing values will not be imputed and this participant will be removed from the analysis of the corresponding variable, i.e., it might be that the number of participants providing data to an analysis is smaller than the number of participants in the FAS.

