12.5 Analysis of secondary endpoints/estimands

12.5.1 Efficacy and/or Pharmacodynamic endpoint(s)

The secondary efficacy variables are described below. Secondary efficacy variables will be analyzed using the FAS population. Handling of missing data for secondary variables will be the same as for the primary variable.

ACR50 at Week 16

Response at Week 16 to ACR50 in the FAS will be evaluated using a logistic regression model with treatment group as a factor and weight as a covariate.

DAS28-CRP at Week 16

Between-treatment differences in the change from BSL in DAS28-CRP will be evaluated using MMRM with treatment group and analysis visit as factors and BSL DAS28-CRP score and weight as continuous covariates. Treatment by analysis visit and BSL DAS28-CRP score by analysis visit will be included as interaction terms in the model. An unstructured covariance structure will be assumed for the model.

PASDAS at Week 16

Between-treatment differences in the change from BSL in PASDAS will be evaluated using MMRM with treatment group and analysis visit as factors and BSL PASDAS score and weight as continuous covariates. Treatment by analysis visit and BSL PASDAS score by analysis visit will be included as interaction terms in the model. An unstructured covariance structure will be assumed for the model.

SF-36 PCS at Week 16

See Section 12.5.7 PROs.

Physical function (HAQ-DI[©]) at Week 16

Between-treatment differences in the change from BSL in HAQ-DI[©] will be evaluated using MMRM with treatment group and analysis visit as factors and BSL HAQ-DI[©] score and weight as continuous covariates. Treatment by analysis visit and BSL HAQ-DI[©] score by analysis visit will be included as interaction terms in the model. An unstructured covariance structure will be assumed for the model.

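### Does SF-36 PCS at Week 16 lack a between-arm analysis because Protocol 12.5.1 points to a section that cannot be found?

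*Protocol*

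**What the plan says.** Table 2-1 of the protocol names the endpoint: "Change from BSL in SF36-PCS at Week 16". Section 2.2 states its clinical question as the effect of secukinumab "versus placebo on change from BSL in SF-36 PCS at week 16 in Chinese patients with active PsA had patients completed" the 16 weeks of treatment. One estimand serves all continuous secondary variables, with this summary: "Population-level summary: difference in variable means between secukinumab and placebo groups".

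Section 12.5.1 then describes the analyses. DAS28-CRP, PASDAS and HAQ-DI each have a full model paragraph; the first begins "Between-treatment differences in the change from BSL in DAS28-CRP will be evaluated using MMRM with treatment group and analysis visit as factors". Under the PCS heading there is one line: "See Section 12.5.7 PROs". The contents list 12.5.1 to 12.5.3, then one blanked entry, then 12.7, and the body follows the same order. The patient-reported outcomes section is 12.5.3, where the visible PCS sentence is "For the change in SF-36 summary scores (PCS), summary statistics will be provided using observed data for each treatment regimen".

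Three other places bear on the point:

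- Protocol 12.4.3 gives a general rule: "Continuous variables (e.g., ACR components, etc.) will be analyzed using a mixed-effects model repeated measures (MMRM"), under a missing-at-random assumption and without single-value imputation.
- The data analysis part of the protocol summary says "Full details of data analysis will be specified in statistical analysis plan".
- SAP 2.6.1 lists change in SF36-PCS among the secondary endpoints. SAP 2.6.2 says the models for the secondary objectives were set out in the SAP for the primary endpoint analysis.

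**The concern.** PCS is the only one of the four continuous secondary endpoints without its own visible model. The pointer that should lead to one leads nowhere, and the section it probably means offers one summary per regimen on observed data. Two per-arm means are not an estimated difference with an interval. Subtracting one from the other would give an unadjusted observed-case contrast, whereas Section 2.2 asks what would have happened had everyone completed 16 weeks.

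This matters more in a study that relies on estimation instead of formal testing (Protocol 12.8.1), because the main product of a secondary endpoint is then its estimated difference and confidence interval. If PCS really were summarised only arm by arm, one stated objective would go unanswered, or the choice of model would be left until after the data were seen.

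**Working it through.** The plan gives no figure for PCS; Table 12-1 concerns ACR20 only. The check is therefore mainly a comparison of the texts.

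**1. The pointer.** The target is described as the PRO section, and the PRO section can be read at 12.5.3. The number 12.5.7 looks like a leftover from another numbering. The reader still reaches the right place by title.

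**2. Which rule covers PCS.**

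| Question | Text that answers it | Does it reach PCS? |
|---|---|---|
| Method for continuous variables | Protocol 12.4.3, MMRM | Yes: PCS change is continuous, and the examples given are not a closed list |
| Missing data for secondary variables | Protocol 12.5.1 and SAP 2.6.1, same as for the primary variable | Yes: all secondary variables |
| Quantity to estimate | Protocol 2.2, one estimand for continuous secondaries | Yes: PCS has its own question there |
| Full model statement | SAP 2.6.2, in the primary-endpoint SAP | Yes: PCS is on the list in SAP 2.6.1 |

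The PCS sentence in 12.5.3 does not mention Week 16, does not say that summaries are the only analysis, and does not set 12.4.3 aside. The two fit together as a model for the endpoint and descriptive tables for the questionnaire.

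**3. The unstated terms.** The three written models share one template: treatment and visit as factors, the endpoint's baseline value and weight as covariates, treatment-by-visit and baseline-by-visit interactions, and unstructured covariance. For PCS only the baseline variable changes. Table 8-1 schedules SF-36 at baseline and Weeks 4, 8, 12 and 16, so the template can be applied to data already collected.

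**4. The SAP wording.** SAP 2.8 has the same descriptive sentence for PCS. But SAP Section 1 says this version covers the final database lock and does not repeat Week 16 analyses, and SAP 2.1 says later data are generally summarised descriptively. A descriptive PCS table is what one expects there. It is not evidence of how the Week 16 comparison was done.

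**5. Redaction.** An emptied bullet stands directly above the PCS sentence in Protocol 12.5.3. In SAP 2.8 the sentence contains a redaction and is followed by a redacted block. The absence of visible PCS model text cannot be read as absence from the plan.

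**6. Size under the worst reading.** Suppose only the unadjusted difference of observed changes were used. Take n = 20 per arm (Protocol 12.8.1), complete data, and an assumed baseline-to-Week-16 correlation ρ of 0.3 to 0.7, which the documents do not give. In units of the PCS standard deviation, with weight left out, the 95% half-widths are:

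- unadjusted: t(38) × √(2(1 − ρ)) × √(2/20)
- baseline-adjusted: t(37) × √(1 − ρ²) × √(2/20) × √(1 + 1/37)

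with t(38) = 2.024 and t(37) = 2.026.

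| ρ | Unadjusted | Adjusted | Narrower by |
|---|---|---|---|
| 0.3 | 0.757 | 0.619 | 18.2% |
| 0.5 | 0.640 | 0.562 | 12.2% |
| 0.7 | 0.496 | 0.464 | 6.5% |

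For ρ = 0.5: 2.024 × 1 × 0.3162 = 0.640, and 2.026 × 0.8660 × 0.3162 × 1.0134 = 0.562. Even on that reading, the cost with complete data is some precision on one secondary endpoint.

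**The case for a change.** The best counter-argument is that a specific statement normally overrides a general one. The sentence in 12.5.3 is specific to PCS, while 12.4.3 is a missing-data paragraph under the primary endpoint and does not name PCS. Nor does being patient-reported explain the difference: HAQ-DI is also listed as a PRO in Protocol 8.5.1.2 and has its own model in 12.5.1. The SAP says analyses follow it together with Section 12 of the protocol, and its list of departures from the protocol (SAP Section 4) covers only the criteria for notable blood pressure and laboratory values. The primary-endpoint SAP cannot be inspected, so its content has to be taken on trust.

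Part of this stands. The section number is wrong, and no list of PCS model terms can be cited from these two documents. SAP 2.6.3, headed for missing values, also repeats the model sentence of 2.6.2, which is a second slip of the same kind. The stronger claim, that no PCS estimate was planned, does not stand. An override needs two statements that conflict, and a descriptive summary does not conflict with a model. SAP 2.6.2 also states positively that the models exist, for a list that includes PCS.

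How to treat values recorded after stopping treatment is a fair question under the Section 2.2 estimand. It applies equally to all four continuous secondary endpoints and is not a PCS gap.

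**Conclusion.** The concern does not hold as a defect in the analysis. Followed as written, with the general MMRM rule, the common estimand and the reference to the earlier SAP, the plan leads to a Week 16 between-arm PCS estimate of the same kind as for DAS28-CRP, PASDAS and HAQ-DI. What is left is a clerical cross-reference error, and unstated terms for one of four continuous secondary endpoints where the template is plain.

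This rests on two things: reading 12.4.3 as covering every continuous efficacy variable, which its wording supports, and accepting SAP 2.6.2's statement about a document not reviewed here. If both failed, the loss with complete data would be an interval roughly 6% to 18% narrower than the unadjusted one, under the assumed correlations. The primary ACR20 analysis, the sample size and data collection are unaffected in either case.

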12.7 Interim analyses

Interim analysis is not applicable in this study.

| Novartis | Confidential | Page 86 of 106 |
|--|--------------|------------------------------|
| Clinical Trial Protocol (Version No. 00) | | Protocol No. CAIN457F2367 |

The primary endpoint analysis will be performed after all participants have completed the Week 16 visit or discontinued earlier. The primary endpoint analysis will be used for regulatory submission. The investigators, site personnel and monitors will continue to remain blinded to the original treatment assignment that each participant received at randomization until after the database lock for Week F60 analysis.

Subsequent to the primary endpoint analysis, the final analysis is planned after participants have completed the Week F60 assessments and may be used for regulatory submission and/or publication purposes. Additional analyses may be performed to support interactions with health authorities, as necessary.

12.8 Sample size calculation

12.8.1 **Primary endpoint(s)**

As it is a bridging study for China registration, this study will pursue an estimation strategy rather than formal hypothesis testing of treatment difference.

Analysis of the pooled data of global pivotal studies (CAIN457F2312, CAIN457F2318, CAIN457F2336 and CAIN457F2342) showed an active drug response rate of about 51.4% and a placebo response rate of 23.1% after 16 weeks for ACR20. With 40 participants (1:1 ratio to two arms), there are approximately 86.0% probability to show at least 50% global treatment difference (14.15%) and approximately 96.0% probability to show positive treatment difference.

Table 12-1 shows the probability of success with different observed response rates.

| | | | | | | - | | |
|------------|-----------------------------------|------------------|------------------------|----------------------|----------------------------------|-------|----------------------------------|-------|
| | Observed Res | ponse Rat | е | | Criterion 1 | | Criterion 2 | |
| | Secukinuma b (p ₁) | Placeb o (p₂) | p 1 -p 2 | 95% CI of (p1-p2) | Aimed Treatment Difference | PoS | Aimed Treatment Difference | PoS |
| Scenario 1 | 0.464 | 0.231 | 0.233 | (-0.053, 0.519) | > 0.1415 | 0.772 | > 0 | 0.922 |
| Scenario 2 | 0.514 | 0.231 | 0.283 | (-0.003, 0.569) | > 0.1415 | 0.860 | > 0 | 0.960 |
| Scenario 3 | 0.564 | 0.231 | 0.333 | (0.048, 0.618) | > 0.1415 | 0.922 | > 0 | 0.981 |
| Scenario 4 | 0.614 | 0.231 | 0.383 | (0.101, 0.665) | > 0.1415 | 0.961 | > 0 | 0.992 |

 Table 12-1
 Probability of Success with Different Observed Response Rates

13 Ethical considerations and administrative procedures

13.1 Regulatory and ethical compliance

This clinical study was designed and shall be implemented, executed and reported in accordance with the ICH Harmonized Tripartite Guidelines for Good Clinical Practice, with applicable local regulations (including European Directive 2001/20/EC, US CFR 21), and with the ethical principles laid down in the Declaration of Helsinki.

13.2 Responsibilities of the investigator and IRB/IEC

Before initiating a trial, the investigator/institution must obtain approval/favorable opinion from the Institutional Review Board/Independent Ethics Committee (IRB/IEC) for the trial protocol, written informed consent form, consent form updates, participant recruitment procedures (e.g., advertisements) and any other written information to be provided to participants. Prior to study start, the investigator is required to sign a protocol signature page confirming his/her agreement to conduct the study in accordance with these documents and all of the instructions and procedures found in this protocol and to give access to all relevant data and records to Novartis monitors, auditors, Novartis Quality Assurance representatives, designated agents of Novartis, IRBs/IECs, and regulatory authorities as required. If an inspection of the clinical site is requested by a regulatory authority, the investigator must inform Novartis immediately that this request has been made.

13.3 Publication of study protocol and results

The protocol will be registered in a publicly accessible database such as clinicaltrials.gov and as required by local regulation. In addition, after study completion and finalization of the study report the results of this trial will be submitted for publication and posted in a publicly accessible database of clinical trial results, such as the Novartis clinical trial results website and all required Health Authority websites (e.g., Clinicaltrials.gov).

For details on the Novartis publication policy including authorship criteria, please refer to the publication policy training materials that will be provided to you at the investigator portal.

13.4 Quality Control and Quality Assurance

Novartis maintains a robust Quality Management System (QMS) that includes all activities involved in quality assurance and quality control, to ensure compliance with written Standard Operating Procedures as well as applicable global/local Good Clinical Practice (GCP) regulations and ICH Guidelines.

Audits of investigator sites, vendors, and Novartis systems are performed by auditors, independent from those involved in conducting, monitoring or performing quality control of the clinical trial. The clinical audit process uses a knowledge/risk based approach.

Audits are conducted to assess GCP compliance with global and local regulatory requirements, protocols and internal SOPs, and are performed according to written Novartis processes.

14 Protocol adherence

This protocol defines the study objectives, the study procedures and the data to be collected on study participants. Additional assessments required to ensure safety of participants should be administered as deemed necessary on a case by case basis. Under no circumstances including incidental collection is an investigator allowed to collect additional data or conduct any additional procedures for any purpose involving any investigational drugs under the protocol, other than the purpose of the study. If despite this interdiction prohibition, data, information, observation would be incidentally collected, the investigator shall immediately disclose it to

Novartis and not use it for any purpose other than the study, except for the appropriate monitoring on study participants.

Investigators ascertain they will apply due diligence to avoid protocol deviations. If an investigator feels a protocol deviation would improve the conduct of the study this must be considered a protocol amendment, and unless such an amendment is agreed upon by Novartis and approved by the IRB/IEC and Health Authorities, where required, it cannot be implemented.

14.1 **Protocol amendments**

Any change or addition to the protocol can only be made in a written protocol amendment that must be approved by Novartis, health authorities where required, and the IRB/IEC prior to implementation.

Only amendments that are required for participant safety may be implemented immediately provided the health authority are subsequently notified by protocol amendment and the reviewing IRB/IEC is notified.

16.1 Appendix 1: Clinically notable laboratory values and vital signs

The following criteria will be used to define expanded limits and notable abnormalities of key laboratory tests.

| Laboratory variable | Standard units | SI units | | | | |
|---|-----------------------------------|----------------------------|--|--|--|--|
| Liver function and related vari | ables | | | | | |
| Serum Glutamic Oxaloacetic Transaminase (SGOT) (AST) | ≥ 3 × upper limit of normal (ULN) | ≥ 3 × ULN | | | | |
| Serum Glutamic Pyruvic Transaminase (SGPT) (ALT) | ≥ 3 × ULN | ≥ 3 × ULN | | | | |
| Bilirubin | ≥ 2 × ULN | ≥ 2 × ULN | | | | |
| Alkaline phosphatase | ≥ 2 × ULN | ≥ 2 × ULN | | | | |
| GGT | ≥ 2 × ULN | ≥ 2 × ULN | | | | |
| Renal function, metabolic and | electrolyte variables | | | | | |
| Urea | ≥ 5 × ULN | ≥ 5 × ULN | | | | |
| Creatinine | ≥ 3 mg/dL | ≥ 265 µmol/L | | | | |
| Uric acid | M ≥ 12 mg/dL | M ≥ 714 µmol/L | | | | |
| | F≥9 mg/dL | F ≥535 µmol/L | | | | |
| Glucose | < 45 mg/dL | < 2.5 mmol/L | | | | |
| | > 250 mg/dL | > 13.9 mmol/L | | | | |
| Cholesterol | ≥ 350 mg/dL | ≥ 9.1 mmol/L | | | | |
| Triglycerides | ≥ 750 mg/dL | ≥ 8.5 mmol/L | | | | |
| CK (MB) | None | None | | | | |
| Potassium | < or = 3.0 mEq/L | < or = 3 mmol/L | | | | |
| | < or = 6.0 mEq/L | > or = 6 mmol/L | | | | |
| Calcium | < or = 6 mg/dL | < or = 1.5 mmol/L | | | | |
| | > or = 13 mg/dL | > or = 3.2 mmol/L | | | | |
| Magnesium | < 1.0 mg/dL | < 0.4 mmol/L | | | | |
| | > 3.6 mg/dL | > 1.5 mmol/L | | | | |
| Amylase | ≥ 2 x ULN | ≥ 2 x ULN | | | | |
| Lipase | ≥ 2 x ULN | ≥ 2 x ULN | | | | |
| Hematology variables | Hematology variables | | | | | |
| Hemoglobin | < 7 g/dL | < 4.39 mmol/L | | | | |
| Platelets (thrombocytes) | < 50 k/mm ³ | < 50 × 10 ⁹ /L | | | | |
| | ≥ 700 k/mm³ | ≥ 700 × 10 ⁹ /L | | | | |
| Leukocytes (WBCs) | ≤ 2.0 k/mm ³ | ≤ 2.0 × 10 ⁹ /L | | | | |
| | ≥ 16 k/mm³ | ≥ 16 × 10 ⁹ /L | | | | |

| Table 16-1Clinically notable laboratory values and vital signal | jns |
|---|-----|
|---|-----|

| Laboratory variable | Standard units | SI units | | | |
|---|---|--------------------------|--|--|--|
| Liver function and related var | Liver function and related variables | | | | |
| Hematology variables: Differe | ntial | | | | |
| Granulocytes (poly, neutrophils) | ≤ 1,000/mm ³ | ≤ 1 x 10 ⁹ /L | | | |
| Eosinophils | ≥ 12% | ≥ 12% | | | |
| Lymphocytes | ≤ 1,000/mm ³ | ≤ 1 × 10 ⁹ /L | | | |
| Vital sign variables | Notable criteria | | | | |
| Systolic Blood Pressure (BP) (mm/Hg) | Either an increase of \ge 30 that results in \ge 180 or $>$ 200 (mm/Hg) OR a decrease of \ge 30 that results in \le 90 or $<$ 75 (mm/Hg) | | | | |
| Diastolic BP (mm/Hg) | Either an increase of \ge 20 that results in \ge 105 or $>$ 115(mm/Hg) OR a decrease of \ge 20 that results in \le 50 or $<$ 40 (mm/Hg) | | | | |

